8.3. Variables

8.3.1. Definitions

The following definitions apply to data collection:

- **Treatment discontinuation** is defined as a recorded clinician decision (with an associated decision date) to permanently discontinue mepolizumab treatment.
- **Treatment interruption** is defined as withholding ≥ 1 mepolizumab dose for any reason without a confirmed clinician decision to permanently discontinue treatment or initiate a new line of treatment.
- **Treatment delay** is defined as a delay (intentionally or unintentionally) in receiving mepolizumab without skipping a dose.

8.3.2. Baseline Characteristics

Baseline characteristic data at the date of the first mepolizumab dose (i.e., the index date) or up to 12 months prior to the first mepolizumab dose (i.e., the pre-index period) will be extracted if available from routine care visits at study enrolment.

The following data will be recorded where available:

- Demographics:
 - Age (at diagnosis, at mepolizumab initiation and at enrolment)
 - Sex
 - Race/ethnicity
 - Height/weight at mepolizumab initiation
- Clinical characteristics at diagnosis (most recent data available up to 12 months before or at diagnosis):
 - EGPA disease characteristics
 - Asthma with eosinophilia
 - Neuropathy
 - Pulmonary infiltrates
 - Sinonasal abnormality
 - Cardiomyopathy
 - Palpable purpura
 - ANCA-positive status
- Clinical characteristics at the index date (most recent data available up to 12 months before or at initiation of mepolizumab):
 - Absolute eosinophil count
 - EGPA disease status (remission, relapsing, refractory) according to European League Against Rheumatism (EULAR) criteria [[Hellmich, 2007](#)], if feasible, or to local standard practice
 - EGPA disease features based on the Chapel Hill Consensus Conference (CHCC) 2012 nomenclature system [[Jennette, 2013](#)]
 - Comorbidities at the index date (most recent data available up to 12 months before or at the index date)
- Treatment history regarding EGPA disease management (specifically OCS and immunosuppressants) and concomitant medications 12 months prior to the index date: type(s), start date(s), dose(s) and formulation(s)
- Additional variables to extract, if data is available:
 - EGPA American College of Rheumatology (ACR)/Lanham criteria at diagnosis
 - Asthma exacerbations prior to the index date defined as exacerbations of bronchial asthma which require hospitalisation, an emergency room visit or use of systemic steroids (any increase in dose that are higher than the maintenance OCS dose)
 - PVAS and PVDI score at the index date
 - Spirometry measurement results (FEV1) at the index date (most recent data available up to 12 months before or at the index date)
 - Hospital admissions at the index date (number, length of stay, primary reason for hospitalisation, ward type[s])

The World Health Organization (WHO) Drug Dictionary for medications will be used for coding drugs. The Medical Dictionary for Regulatory Activities (MedDRA) will be used for coding concomitant diseases.

8.3.3. Mepolizumab Treatment, Comorbidities and Concomitant Medications

Mepolizumab, comorbidities and concomitant medication data during the follow-up period will be extracted from medical records from routine care visits before or after enrolment depending on when a patient initiated mepolizumab.

The following data will be recorded where available:

- Mepolizumab treatment details:
 - Dates of administration
 - Dose
 - Formulation
 - Treatment setting (e.g., in-clinic, at home)
 - Reason for initiation of mepolizumab
 - Treatment changes (dose delays/interruptions, dose changes, discontinuation) and reasons
- Concomitant Medications (OCS, immunosuppressant and other):
 - Dates of administration
 - Dose
 - Formulation
 - Reason for initiation
 - Treatment changes (dose changes, discontinuation) and reasons
- Comorbidities during follow-up

8.3.4. Safety

8.3.4.1. Adverse Events (AEs), Serious Adverse Events (SAEs) and Other Safety Reporting

The definitions of AEs, SAEs, pregnancy exposures, adverse drug reactions (ADRs) and medical device incidents (including malfunctions) can be found in Section 10.1.

All AEs, SAEs, pregnancy exposures and medical device incidents that occur during and/or after administration of mepolizumab, regardless of a causal relationship to mepolizumab, will be recorded (coded using the MedDRA classification) in the eCRF. This will include recording information on seriousness, severity, action taken (with AE-related drugs coded using the WHO Drug Dictionary), and relationship to mepolizumab.

For AEs/SAEs, investigators will also need record in the eCRF if the event was related to a GSK product other than mepolizumab; details of the GSK product will be recorded in the Concomitant Medications page of the eCRF.

Medical device incidents related to mepolizumab will be recorded on the Medical Device Incident Form (Section 10.3).

Safety data during the follow-up period will be extracted from medical records from routine care visits before or after enrolment depending on when a patient initiated

mepolizumab. Timelines for reporting safety events during prospective follow-up (i.e., from enrolment until the end of follow-up) can be found in Section 10.3.

If an event is observed that is considered related to a drug product from another Sponsor (i.e., not GSK), the Investigator is advised to report the event to the appropriate marketing authorization holder of the suspected medicinal product or to the concerned competent authority via the national spontaneous reporting system.

8.3.4.2. Adverse Events of Special Interest

Adverse events of special interest (AESI) include the following and these events will be subject to additional data collection within AE / SAE forms within the eCRF.

- Systemic reactions including anaphylaxis

Note: these events will be assessed by the Investigator as to whether they meet the diagnostic criteria for anaphylaxis as outlined by the 2006 Joint NIAID/FAAN Second Symposium on Anaphylaxis [Sampson, 2006] (See Section 10.2).

- Local injection site reactions

8.3.4.3. Time Period and Frequency for Collecting AE and SAE Information

The Investigator or their designee will collect AE, SAE, pregnancy exposures and medical device incident information during the follow-up period.

All SAEs occurring at or after patient enrolment will be recorded and reported to the Sponsor or designee immediately and under no circumstance should this exceed 24 hours, as indicated in Section 10.3. The Investigator will send data to GSK within 24 hours of it being available. Safety data extracted retrospectively up to enrolment from patients who initiated mepolizumab up to 12 months prior to enrolment will be summarised in study reports only.

Investigators are not obligated to actively seek information on AEs or SAEs after the conclusion of the study participation. However, if the Investigator learns of any SAE, including a death, at any time after a patient has been discharged from the study, and he/she considers the event to be reasonably related to the study intervention or study participation, the Investigator must promptly notify the Sponsor.

8.3.4.4. Follow-up of AEs and SAEs

After the initial AE/SAE report, the Investigator is required to proactively follow each patient at subsequent visits/contacts. All AEs, SAEs and medical device incidents (as defined in Section 10.1) will be followed until the event is resolved or stabilised, or until the last study visit within routine care; whichever comes first.

8.3.4.5. Pregnancy

Details of all pregnancies in female patients will be extracted during the follow-up period. There is no requirement to collect pregnancy information from female partners of male patients.

While pregnancy itself is not considered to be an AE or SAE, any pregnancy complication or elective termination of a pregnancy for medical reasons is required to be reported as an AE or SAE. Abnormal pregnancy outcomes (e.g., spontaneous abortion, foetal death, stillbirth, congenital anomalies, ectopic pregnancy) are considered SAEs and will be reported as such.

Timelines for reporting pregnancies from enrolment until the end of follow-up can be found in Section 10.3. Pregnancy data collected up to enrolment from patients who initiated mepolizumab up to 12 months prior to enrolment will be summarised in study reports only.

The patient will be followed to determine the outcome of the pregnancy. The Investigator will collect follow-up information on the patient and the neonate, and the information will be forwarded to the Sponsor. Any post-study pregnancy-related SAE considered reasonably related to a GSK product by the Investigator will be reported to the Sponsor. While the Investigator is not obligated to actively seek this information in former study patients, he or she may learn of an SAE through spontaneous reporting.

8.3.4.6. Medical Device Incidents (Including Malfunctions)

Mepolizumab solutions are delivered via medicine/medical device combination products (pre-filled syringe/pen/auto injector). To fulfil regulatory reporting obligations worldwide, the investigator is responsible for the detection and documentation of events meeting the definitions of device deficiency that occur during the study with such devices.

The definition of a medical device incident can be found in Section 10.1. **Note:** deficiencies fulfilling the definition of an AE/SAE will also follow the processes outlined in Section 10.2 and Section 10.3 of the protocol.

Timelines for reporting medical device incidents from enrolment until the end of follow-up can be found in Section 10.3. Medical device incidents collected prior to enrolment from patients who initiated mepolizumab up to 12 months prior to enrolment will be summarised in study reports only.

8.3.5. Physician Narrative/Opinion

Physicians will provide a narrative/opinion on the benefit/risk profile of mepolizumab after the last study visit within routine care of each patient.

8.3.6. Additional Variables

The following variables assessed during the follow-up period will also be extracted from medical records from routine care visits before or after enrolment depending on when a patient initiated mepolizumab, if data is available:

- EGPA disease features based on the CHCC 2012 nomenclature system [[Jennette, 2013](#)] including respiratory and cardiac involvement during follow-up
- Absolute eosinophil counts
- EGPA disease status (remission, relapse or refractory) compared to previous visit according to EULAR criteria [[Hellmich, 2007](#)], if feasible, or to local standard practice
- Asthma exacerbations since last routine care visit defined as exacerbations of bronchial asthma which require hospitalisation, an emergency room visit or use of systemic steroids
- PVAS and PVDI scores recorded during follow-up
- Spirometry measurement (FEV1) recorded during follow-up
- Hospital admissions during follow-up
 - Admission and discharge date(s) since last routine care visit
 - Primary reason for hospitalisation

The PVAS is a 10-item, validated, clinician-completed tool used for the assessment of disease activity in systemic vasculitis divided into organ-based systems, with each section including symptoms/signs that are typical of that particular organ involvement in systemic vasculitis [[Dolezalova, 2013](#)]. Scores range from 0 to 63, depending on the existence or absence of clinical items for active vasculitis after excluding other causes (such as infection). The higher the score, the stronger the disease activity, with >5 points indicating vasculitis activity and ≥ 25 points indicating a high activity. Where available, PVAS scores will be extracted into the CRF.

The PVDI is a 72-item clinician-completed tool (not validated yet) to assess vasculitis damage defined as the presence of irreversible features present for at least 3 months since the onset of vasculitis [[Dolezalova, 2014](#)]. Where available, the total PVDI score will be extracted into the CRF.

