8.1.1. Definitions

The following definitions apply to the design of the study:

- **Index date** is defined as the date of the first (non-missing) dose of mepolizumab.
- The **pre-index period** for data collection is defined as up to 12 months prior to the index date.
- **Study period is up to 36 months.** It spans from 12 months before the index date, i.e., for collecting available demographic and relevant medical history prior to the first dose of mepolizumab until the end of the follow-up period.
- **Follow-up period is up to a maximum of 24 months.** Depending on the time point of initiating mepolizumab treatment in relation to the enrolment start date, data will be collected either prospectively and/or retrospectively until 24 months after the index date, or study discontinuation for any reason, or up to 12 months after mepolizumab treatment discontinuation; whichever comes first.

Figure 1 shows the study workflow scenarios in detail for patients who initiated mepolizumab prior to or at enrolment.

Figure 1 Study Workflow Patient Scenarios

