8.7.2.3. Analysis of Secondary Objectives

The secondary objective for the study is to characterise paediatric EGPA patients treated with mepolizumab per routine clinical care in terms of demographics, clinical characteristics, medical and treatment history as well as real-world effectiveness of mepolizumab treatment in terms of the effect of mepolizumab on OCS dosage.

The following data will be described per SP patient **during the pre-index period**:

- Age (years) at diagnosis, mepolizumab initiation and enrolment
- Sex
- Ethnicity/Race
- Details of EGPA (symptoms and severity) at diagnosis, and at initiation of mepolizumab (EGPA status and duration of EGPA)
- EGPA management and concomitant medications (past 12 months)
- Absolute eosinophil count
- Comorbidities
- Additional variables to be described, if data is available:
 - EGPA American College of Rheumatology (ACR)/Lanham criteria at diagnosis
 - Number of asthma exacerbations (past 12 months)
 - PVAS and PVDI score at the index date
 - Baseline spirometry measurements (FEV1)
 - Number of hospital admissions (past 12 months) and length of stay

The following data will be described per SP patient according to whether follow-up data was extracted before (retrospective) or after (prospective) enrolment **during the post-index period**:

- Treatment data:
 - Mepolizumab treatment dose, duration of treatment (DoT), setting, formulation and (reasons for) discontinuation, dose delays/interruptions and dose changes
 - Daily OCS dose, DoT per formulation and (reasons for) discontinuation and dose changes
 - Immunosuppressant dose and DoT per type and formulation and (reasons for) discontinuation and dose changes
 - Other treatment type(s), dose(s), DoT and formulation(s)
- Physician narrative/opinion on the benefit/risk profile of mepolizumab including:
 - Comprehensive assessment of mepolizumab effectiveness as “effective”, “not effective” or “indeterminable” (including reasons) during the post-index treatment period (see definition Section 8.3.1).
- Additional outcomes to be described, if data is available:
 - Respiratory and cardiac involvement during follow-up
 - Absolute eosinophil counts (% change of baseline)
 - EGPA disease status (remission, relapse or refractory) during follow-up
 - Change from baseline in asthma exacerbations
 - Change from baseline in PVAS and PVDI
 - Change from baseline in spirometry measurement (FEV1).
 - Annual hospital admissions

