 - Cumulative hospital admission length of stay

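### Asthma exacerbations are defined differently before and after the index date, yet a change from baseline is planned between the two, with no time unit stated

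*Protocol*

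**What the plan says.** The exacerbation definition appears twice in the Protocol. Section 8.3.2 (baseline) and Section 8.3.6 (follow-up) both count an asthma exacerbation that leads to admission, an emergency visit or systemic steroids. They differ on the steroid limb. At baseline it reads "use of systemic steroids (any increase in dose that are higher than the maintenance OCS dose". For follow-up the sentence stops without that limit: "Asthma exacerbations since last routine care visit defined as exacerbations of bronchial asthma which require hospitalisation, an emergency room visit or use of systemic steroids".

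Section 8.7.2.3 then uses both. The pre-index list has "Number of asthma exacerbations (past 12 months"; the post-index list has "Change from baseline in asthma exacerbations", with no time unit.

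The hospital outcomes in the same section are set out differently. Before index: "Number of hospital admissions (past 12 months) and length of stay". After index: "Annual hospital admissions" and "Cumulative hospital admission length of stay". Neither is listed as a change from baseline.

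On the windows, Section 8.1.1 says the pre-index period "is defined as up to 12 months prior to the index date". Follow-up there runs to at most 24 months from the first dose and ends earlier if the patient leaves the study, or 12 months after mepolizumab is stopped for good.

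**The concern.** A before/after difference has meaning only if events are counted by the same rule and over comparable time. Here the rule changes at the index date, which is also the start of treatment, so a shift in what is counted cannot be told apart from a shift in what happened. Section 6.1.2 describes corticosteroids as the mainstay of EGPA treatment, so patients on maintenance OCS, for whom the two wordings differ, are likely to be common in this series.

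The definition governs what sites extract into the eCRF. Once episodes have been recorded under two rules, an analysis plan cannot reliably put them back on one.

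The time base is a second and weaker point. Section 8.7.2.3 puts admissions on a yearly scale and leaves exacerbations without any scale, although the baseline is a 12-month count and follow-up differs between patients. With about 10 patients described one by one, nothing averages out: each patient's figure is the result.

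**Working it through.** The Protocol gives no exacerbation rate and no expected change, so there is no planned figure to reproduce. Its windows are consistent: 12 + 24 = 36 months, the study period in Section 8.1.1. All event rates below are assumptions.

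**1. Where the two definitions differ**

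- Patient not on maintenance OCS: any systemic steroid course is a rise above zero, so the two wordings agree.
- Patient on maintenance OCS, episode with a dose rise, emergency visit or admission: counted under both.
- Patient on maintenance OCS, episode with none of these (for example, one handled by holding the dose rather than raising it): not counted under Section 8.3.2, but can be counted under Section 8.3.6.

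The wordings differ only in the third case, and only in one direction: more can be counted after index.

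**2. Size of the definition effect**

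Let E be the episodes per year, unchanged by treatment, and s the share of the third kind. Counted before index: E(1 − s). Counted after index: at most E, if sites count every such episode. Spurious rise: up to E × s per year. With E = 4 assumed:

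| s | before, per year | after, per year | spurious change |
|---|---|---|---|
| 0 | 4 | 4 | 0 |
| 25% | 3 | 4 | +1 |
| 50% | 2 | 4 | +2 |

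Annualising does not remove this. At s = 25% over 24 months, 8 counted episodes / 2 years = 4 per year, against 3 before: still +1.

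**3. Size of the time-base effect, if raw counts were used**

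Take one definition, a rate r per year that does not change, and T months of follow-up.

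- Raw change = r × T/12 − r
- Rate change = (r × T/12)/(T/12) − r = 0 for every T

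With r = 2 assumed:

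| T (months) | before | after, raw | raw change | rate change |
|---|---|---|---|---|
| 6 | 2 | 1 | −1 | 0 |
| 12 | 2 | 2 | 0 | 0 |
| 18 | 2 | 3 | +1 | 0 |
| 24 | 2 | 4 | +2 | 0 |

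At 24 months the raw change is +1 for r = 1 and +4 for r = 4. If the rate truly halves from 2 to 1 per year, the raw change at 24 months is 1 × 2 − 2 = 0, while the rate change is 1 − 2 = −1 per year.

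**4. Hospital outcomes**

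A constant d hospital days per year gives d in the 12 months before index and 2d accumulated over 24 months after it. The two figures would stand side by side on different time bases, but no difference between them is planned. Admissions after index are already yearly.

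**The case against.** On the definition, the best defence is that Section 8.3.6 counts an exacerbation only if it requires systemic steroids. Background OCS is not required by the exacerbation, so being on it does not by itself meet the limb. On that reading the parenthesis in Section 8.3.2 only clarifies, and its absence later is a drafting slip. This is plausible and limits the likely size: s may be small. It does not remove the point. Sites extract by the wording in front of them, and only the baseline wording tells them how to treat maintenance OCS.

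On the time base, three stronger readings are tempting and the Protocol does not support them.

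- A reader might infer that the change is wrong by construction, because totals over 24 months are subtracted from 12-month counts. Nothing in the Protocol says so. The scale is left open, and the analysis plan, which is not at hand, may annualise.
- A reader might infer that admissions and length of stay share the fault. Admissions are annual, and no change from baseline is planned for either outcome.
- A reader might infer that children who stop mepolizumab early would appear to improve because their follow-up is short. Section 8.1 asks investigators to keep them in the study for up to 12 months after stopping. A child who stops at month t is therefore planned to be followed to about month t + 12, capped at 24, which is at least 12 months. The 6-month row above needs withdrawal from the study or loss to follow-up.

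The defence is also right about rank. The stated effectiveness objective in Section 7.2 is OCS dosage. Exacerbations and hospital stay are additional outcomes, described if available, with no hypothesis tested.

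**Conclusion.** The definition mismatch holds on the text alone: the same outcome has a narrower steroid limb before index than after it, and a change is planned between the two. Its direction is known (against mepolizumab). Its size is not: it is zero for patients without maintenance OCS, and otherwise up to E × s episodes per year, for example +1 per year at an assumed 4 per year with a quarter of episodes affected.

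The time-base point holds only conditionally. The exacerbation change is under-specified, and it would mislead if raw counts were used with follow-up other than 12 months: at an assumed constant 2 per year, +2 at 24 months and 0 at 12. For length of stay it is a matter of presentation.

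The severity is minor, given that these are if-available outcomes in an untested case series of about 10 patients.

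**What to change.** 1. Reconcile Sections 8.3.2 and 8.3.6 so that one exacerbation definition, stating how maintenance OCS is treated, applies in both periods, and carry it into the eCRF.
2. In Section 8.7.2.3, report exacerbations and hospital days per patient-year in each period, with the months observed beside each rate. Define the exacerbation change as the difference of the two rates. The months are needed before index too, since that period is a maximum and not a fixed length.
3. State one window for baseline hospital data. Section 8.3.2 ties admissions to the index date while Section 8.7.2.3 uses the preceding 12 months, and a rate needs a denominator.
4. Leave the annual admissions outcome as it is.

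The cost is small: wording in three sections and one eCRF definition. Follow-up admission and discharge dates are already collected (Section 8.3.6). No event date is specified for exacerbations, but a count and the months observed are enough for a rate. If episodes have already been entered, they need checking against the single definition, for which the OCS doses and dates in Section 8.3.3 and the treatment history in Section 8.3.2 should help.
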